## **9.2 6MWT**

Observed, absolute change from baseline, and percent change from baseline in distance walked in the 6MWT will be listed and summarized. Summary tables will include p-values for treatment group comparisons of changes from baseline. Because of potential differences in 6MWT administration procedures across study sites, “site” will be carefully considered as a potential source of excess variation and will be included in the statistical model as a random effect if warranted. Details from the 6MWT collected on the CRF will be listed.

## **9.3 NYHA Class**

Observed values of New York Heart Association (NYHA) class will be listed and the distribution of change from baseline will be summarized. The summary table will include p-values for treatment group comparisons of distribution.

## **9.4 Quality of Life**

### **9.4.1 MLHFQ**

The MLHFQ was designed to measure physical, emotional, social, and mental quality of life (QoL) dimensions. Subjects are asked to provide a score on a scale from 0 to 5 as to how much each of 21 facets prevented them from living as they desired (0 = “no,” 5 = “very much”). The sum of the 21 scores reflects overall QoL. Although the MLHFQ was not designed to measure any particular dimension separately, two dimensions will be derived: Physical (sum of items 2-7, 12, 13) and Emotional (sum of items 17-21). All 21 items as well as the total score and scores for Physical and Emotional dimensions will be listed. Only the total score and Physical and Emotional dimension scores will be summarized. The summary table will include observed values and changes from baseline and p-values for treatment group comparisons of change from baseline.

Missing values for a given individual score will be imputed as the visit-specific worst observed score among all subjects in the given cohort/stratum if the missing value is in the CAP-1002 group and as the best observed score in the given cohort/stratum among all subjects if the missing value is in the placebo group.

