### 2.3.6 Secondary Efficacy Endpoints

The following secondary efficacy endpoints will be evaluated at 6 and 12 months post IP administration unless otherwise noted:

1. Absolute and relative change from baseline in global LV function measures:
  - a) MRI assessment of LV ejection fraction (LVEF)
  - b) MRI assessment of LV end diastolic volume (LVEDV) and end systolic volume (LVESV) indexed to body surface area (BSA)
2. Absolute and relative change from baseline in structural measures:
  - a) MRI assessment of infarct size as a percent of LV mass
  - b) MRI assessment of infarct size expressed in grams
  - c) MRI assessment of viable mass expressed in grams
  - d) MRI assessment of scar transmurality
3. Absolute and relative change from baseline in regional measures:

- a) MRI assessment of function and structure by segment or groups of segments (e.g., region which received the IP)
- 4. Absolute change from baseline in clinical function/status measures:
  - a) Distance covered in six minute walk test (6MWT)
  - b) Minnesota Living with Heart Failure Questionnaire (MLHFQ) score
  - c) Patient Global Assessment (PGA) score
- 5. Absolute and relative change from baseline in cardiac biomarkers:
  - a) NT-proBNP

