either Month 6 or Month 12 changes from baseline missing, but not both. Therefore, for analyses based on the mITT population, missing data will be addressed using ML. For analyses based on the ITT population, in which some subjects may have both Month 6 and Month 12 changes from baseline missing, multiple imputation will be used based on all observations and will use a fully conditional specification method with 20 burn-in iterations and the regression method of imputation. Variables in the imputer's model will be baseline observation (because baseline is used as a covariate in analyses), Month 6 change from baseline, Month 12 change from baseline, and treatment group. Because the MAR assumption is not testable, and because it seems possible that subjects with poorer outcome may be more likely to miss trial assessments, a sensitivity analysis under a "missing not at random" (MNAR) assumption will be done (for the final analysis only) of the primary efficacy endpoint in which multiple imputation will use the pattern-mixture model approach to address missing values; i.e., the imputation will be based on a pre-specified subset of subjects. For this MNAR analysis, only those subjects who had implantable cardioverter defibrillators (ICDs) inserted during the trial. Because very few missing observations are expected in this trial, 5 imputed data sets will be used for all analyses using multiple imputation.

A closed testing procedure will be used for the primary efficacy analysis only (see [Section 2.3.5](#)) and will be done as follows:

1. Let  $p_f$  and  $p_s$  be the p-values from the tests of the individual null hypotheses involving the full group and the subgroup, respectively; tests will be based on least squares (LS) means comparisons.
2. Let  $t_{max} = \max(t_f, t_s)$ , where  $t_f$  and  $t_s$  are the t-statistics from the full group and subgroup analyses in (1) above.
3. Let  $r$  = the correlation between  $t_f$  and  $t_s$ , estimated by the ratio of SDs of the treatment effect estimates in the full group and subgroup.
4. Let  $p_{inter}$  be the p-value from the test of the intersection hypothesis using Dunnett's test; specifically,  $p_{inter} = 1 - \text{probnorm}(t_{max}, t_{max}, r)$ .

Then, if  $p_{inter} < 0.025$  and either  $p_f < 0.025$  or  $p_s < 0.025$  (with treatment effect favoring CAP-1002), the test of treatment effect for the primary efficacy endpoint will be considered statistically significant.

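### Missing MLHFQ scores are imputed in opposite directions by arm in the main analysis, which biases a two-sided secondary comparison; the size depends on an unstated missing rate

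*SAP*

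**What the plan says.** MLHFQ is a secondary efficacy endpoint (SAP 2.3.6). SAP 9.4.1 describes the instrument: "Subjects are asked to provide a score on a scale from 0 to 5 as to how much each of 21 facets" limited the subject's life. The total is the sum of the 21 items, so it runs from 0 to 105 with higher meaning worse. A Physical score (8 items) and an Emotional score (5 items) are also derived. The summary table carries "p-values for treatment group comparisons of change from baseline".

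On missing data, the section fills a missing individual score, separately at each visit, with the "worst observed score among all subjects in the given cohort/stratum if the missing value is in the CAP-1002 group". For placebo the direction is reversed: the value is imputed "as the best observed score in the given cohort/stratum among all subjects if the missing value is in the placebo group".

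Four other places bear on this rule:

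- SAP 7.5 refers the reader to Sections 8-10 for each endpoint's missing-data handling, so the 9.4.1 rule is the operative one for MLHFQ.
- SAP 9 makes the primary mITT population the main one for secondary endpoints, and states that "for analyses based on the mITT population, missing data will be addressed using ML".
- SAP 7.3 sets two-sided tests at 0.05 as the default; Protocol 9.6.2 sets the same for secondary efficacy.
- SAP 9.4.2 averages the answered SF-36 questions and disregards the unanswered ones, in the same way for both arms.

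**The concern.** The imputed value depends on the arm. Each missing follow-up item raises a CAP-1002 subject's score towards the worst value or lowers a placebo subject's score towards the best. The arms are pushed apart by assignment alone, whatever the subjects would have answered.

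A worst/best rule is a familiar stress test for a claim of benefit. Here it feeds the only MLHFQ estimate and p-value that the SAP specifies. Because the test is two-sided, the rule is not simply cautious: it can hide a real benefit, and it can produce a nominally significant result against CAP-1002 when there is no effect. It also means that MLHFQ scores cannot be completed without the treatment codes.

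**Working it through.** The documents state no MLHFQ effect, SD, power or missing rate, so there is no planned figure to reproduce. The check derives the bias and then asks how often it would give a false finding.

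**Inputs from the documents.** 21 items scored 0-5, 8 in Physical and 5 in Emotional (SAP 9.4.1); 2:1 allocation with up to 93 completers (Protocol synopsis), taken as 62 v 31; two-sided 0.05 (SAP 7.3); baseline as covariate (SAP 9).

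**Assumptions.** SD of 15, 20 or 25; a fraction m of follow-up items missing, equal in both arms; no true effect; both item extremes, 0 and 5, observed in each stratum.

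**Bias.** Let μ be the mean item score. A missing item adds on average 5 − μ in CAP-1002 and removes μ − 0 in placebo. The false difference in total score is

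21 × m × [(5 − μ) + (μ − 0)] = 105 × m, whatever μ is.

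- m = 1%: 1.05 points. m = 2%: 2.10. m = 5%: 5.25.
- At m = 5%, Physical shifts by 40 × 0.05 = 2.0 and Emotional by 25 × 0.05 = 1.25.
- If 10% of subjects in each arm skip one item, m = 0.10/21, and the shift is 105 × 0.10/21 = 0.5 points.

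**False significant harm (nominal 2.5%).** SE = SD × √(1/62 + 1/31) = 0.22 × SD, which gives 3.3, 4.4 and 5.5. The probability is 1 − Φ(1.96 − 105m/SE).

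| m | Shift | SD 15 | SD 20 | SD 25 |
|---|---|---|---|---|
| 1% | 1.05 | 5.0% | 4.3% | 3.8% |
| 2% | 2.10 | 9.3% | 6.9% | 5.7% |
| 5% | 5.25 | 35.6% | 22.2% | 15.7% |

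**Check by simulation.** The rule was applied item by item (62 v 31, two strata, total-score SD about 20, change adjusted for baseline, no true effect, 1,500 trials per case). At 1%, 2% and 5% missing, the shifts were 0.97, 1.98 and 5.07 points and false harm was 5.1%, 8.9% and 36.9%. With nothing missing, false harm was 2.5% and false benefit 2.7%. The agreement with the SD 15 column is expected, since adjusting for baseline brings the residual SD below 20.

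**Baseline items.** The rule is visit-specific and does not exclude baseline. With only baseline items missing, the sign reverses: −1.4 points at 2% and −3.5 at 5%, with false benefit in 6.3% and 16.7% of trials. With equal rates at baseline and follow-up, the net shift is still against CAP-1002: +0.6 at 2% and +1.8 at 5%.

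**The case against.** The strongest reply is that the rule is conservative for a superiority claim, touches one secondary endpoint without multiplicity control, and will seldom be used, because SAP 9 expects very few missing observations. The limits on importance stand. Conservatism does not answer a two-sided test, and a rule expected to matter little is no reason to keep a biased one as the main analysis. SAP 9 allows optional analyses in other populations, but none of them removes the item rule.

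Some stronger readings are tempting and are not supported.

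- *A bias of 10.5 points, with false harm in about half of trials.* A reader might put the design's 10% non-completion into 105 × m; simulating wholly missing questionnaires at 10% does give 9.7 points and 50% false harm. But that 10% concerns complete 12-month data. In context, an individual score most naturally means one skipped item. The mITT population is specific to each parameter (SAP 6), so a subject with no post-baseline MLHFQ leaves the analysis and is not imputed.
- *A flat contradiction with ML.* SAP 9 applies ML to a missing Month 6 or Month 12 change. If 9.4.1 covers only skipped items, the two rules work at different levels and can coexist, although the biased totals then enter the ML model. They conflict only if 9.4.1 also covers a wholly missing questionnaire, and the text does not settle this.
- *One missing item in each arm moves the arms 5 points apart.* Five points is the combined change in two subjects' totals. With 69 v 34 randomized, the difference in arm means moves by (5 − μ)/69 + μ/34, which is 0.07 to 0.15 points.
- *Always towards harm.* Missing baseline items act in the opposite direction.
- *Quality of life cannot be assessed.* This does not follow at low missingness, and SF-36, WPAI and PGA do not use this rule.

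**Conclusion.** The point holds as a defect of the written rule: the main MLHFQ comparison depends on arm-specific imputation, with no neutral analysis beside it. For missing follow-up items, or equal rates at baseline and follow-up, the bias runs against CAP-1002. Its size cannot be fixed from the documents. It is negligible if a few subjects skip one item each. It becomes material at a few percent of items: at 2% missing, false harm is already 5.7-9.3% over the SD range considered. These figures rest on equal missingness by arm, no true effect, observed extremes of 0 and 5, and assumed SDs. Trial success depends only on infarct size, so this should be corrected but does not threaten the primary conclusion.

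**What to change.** Reword the missing-data paragraph of SAP 9.4.1 so that the main analysis treats both arms alike:

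1. Prorate the total from the subject's answered items among all 21, and each dimension score from the answered items in that dimension, when at least half are answered (11 of 21, 4 of 8 Physical, 3 of 5 Emotional). The total needs its own rule because items 1, 8-11 and 14-16, eight of the 21, belong to neither dimension.
2. Otherwise, including for a wholly missing questionnaire, leave the score missing and let the ML model of SAP 9 handle it. This also settles the scope question. State that the same rule applies at baseline.
3. Keep worst/best imputation only as a labelled extreme sensitivity analysis.

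With equal missingness and no true effect, an arm-neutral rule has an expected false difference of zero. The cost is SAP wording and one extra sensitivity table; no data collection changes.

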### **9.4.2 SF-36 Health Survey (v1.0)**

The Short Form 36 (SF-36) Health Survey consists of subject responses to 36 questions which are used to derive 8 summary scores, or “scales”: physical functioning, physical health, emotional problems, energy/fatigue, emotional well-being, social functioning, pain, and general health. Therefore, while all 36 questions will be listed, only these 8 scales will be summarized. Summary tables will include observed values, changes from baseline and p-values for treatment group comparisons of change from baseline. The RAND scoring system will be used. In this system, scores from individual questions are averaged to derive scores for the 8 scales; therefore, missing responses to individual questions are ignored.

#### 9.4.3 WPAI:SPH Questionnaire

The Work Productivity and Activity Impairment: Specific Health Problem (WPAI:SPH) questionnaire was designed to measure work and activity impairment due to the specific health problem (for this trial, heart condition) during the past seven days. The instrument yields four types of scores:

1. Absenteeism (work time missed) =

$$\frac{100 \times \# \text{ hours missed due to heart condition (Q2)}}{Q2 + \# \text{ hours missed due to other reasons (Q3)} + \# \text{ of hours actually worked (Q4)}}$$

2. Presenteeism (impairment at work / reduced on-the-job effectiveness) =

$$\frac{100 \times \text{how much did your heart condition affect your productivity while working (Q5)}}{10}$$

3. Work productivity loss (overall work impairment / absenteeism plus presenteeism) =

$$100 \times (\text{Absenteeism} + (1 - \text{Absenteeism}) \times \text{Presenteeism})$$

4. Activity Impairment =

$$\frac{100 \times \text{how much did your heart condition affect your ability to do regular daily activities (Q6)}}{10}$$

WPAI outcomes are expressed as impairment percentages, with higher numbers indicating greater impairment and less productivity. The first 3 summary scores are calculated only for those currently employed.

Each of the 6 WPAI questions will be listed, but only the 4 summary scores detailed above will be summarized. Summary tables will include observed values, changes from baseline and p-values for treatment group comparisons of change from baseline.

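### The WPAI work-productivity-loss score applies on-the-job impairment to hours of unrelated leave, because its weight (1 - Absenteeism) is not the share of time worked when Q3 is above zero

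*SAP*

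**What the plan says.** SAP 9.4.3 derives four WPAI scores. Three matter here.

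- Absenteeism is 100 times "hours missed due to heart condition (Q2") divided by the sum of that item, "hours missed due to other reasons (Q3") and the number "of hours actually worked (Q4").
- Presenteeism is 100 times Q5 divided by 10, where Q5 asks "how much did your heart condition affect your productivity while working (Q5").
- The third score is labelled "Work productivity loss (overall work impairment / absenteeism plus presenteeism"). It is 100 times the sum of Absenteeism and the product of (1 - Absenteeism) and Presenteeism.

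The section restricts these scores to workers: "The first 3 summary scores are calculated only for those currently employed". It also makes them part of the between-group testing: "Summary tables will include observed values, changes from baseline and p-values for treatment group comparisons of change from baseline".

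Protocol 9.6.2 lists change in the WPAI score among the secondary efficacy endpoints. The lists in the protocol synopsis, Protocol 2.4.1 and SAP 2.3.6 do not. Neither document says how Q3 hours should enter the combined score.

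**The concern.** The third score adds time lost through heart-related absence to the reduced output of time spent at work. For that sum to hold, the weight on presenteeism has to be the fraction of time worked. Under the SAP's absenteeism denominator, (1 - Absenteeism) is instead all time not missed for the heart condition, and this includes holidays and other unrelated absence. Impairment at work is then applied to hours when the subject was not at work.

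At stake is the value of one tested patient-reported score. At a given Q2, Q5 and number of scheduled hours, the score cannot tell a subject who worked the remaining hours from one who spent most of them on unrelated leave.

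**Working it through.** The documents give no numerical WPAI result, so there is no figure of the plan's own to reproduce. The check is algebra on the SAP 9.4.3 formulas, followed by illustrative 40-hour weeks. The hours are assumptions, not figures from the documents.

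**Definitions.** Let T = Q2+Q3+Q4, A = Q2/T and P = Q5/10, with A and P as fractions. Fractions are necessary: Absenteeism and Presenteeism are already multiplied by 100, and the third formula multiplies by 100 again. Read literally, Q2=8, Q3=0, Q4=32, Q5=3 gives 100 x (20 + (1 - 20) x 30) = -55,000. That scaling fault is separate and does not depend on Q3.

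**The weight.** 1 - A = (Q3+Q4)/T. The share of time worked is Q4/T. The two are equal only if Q3 = 0.

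**The SAP score.** A + (1 - A)P = [Q2 + (Q3+Q4)P]/T.

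**Two internally consistent targets.** Heart-related hours lost are Q2 + Q4 x P.

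- (i) As a share of all scheduled hours: (Q2 + Q4 x P)/T. The SAP score is too high by Q3 x P/T. It differs only when Q3>0 and Q5>0.
- (ii) As a share of Q2+Q4: (Q2 + Q4 x P)/(Q2+Q4). The SAP score is too low by (1 - P) x [Q2/(Q2+Q4) - Q2/T]. It differs only when Q3>0, Q2>0 and Q5<10.

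Both differences are non-zero when Q2>0, Q3>0 and 0<Q5<10 (taking Q4>0, so that Q5 can be answered).

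**Numbers (percent).**

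| Q2 | Q3 | Q4 | Q5 | SAP score | (i) share of T | (ii) share of Q2+Q4 |
|---|---|---|---|---|---|---|
| 8 | 0 | 32 | 3 | 44.0 | 44.0 | 44.0 |
| 8 | 8 | 24 | 3 | 44.0 | 38.0 | 47.5 |
| 8 | 16 | 16 | 3 | 44.0 | 32.0 | 53.3 |
| 8 | 24 | 8 | 3 | 44.0 | 26.0 | 65.0 |
| 10 | 20 | 10 | 5 | 62.5 | 37.5 | 75.0 |
| 0 | 8 | 32 | 3 | 30.0 | 24.0 | 30.0 |
| 8 | 8 | 24 | 0 | 20.0 | 20.0 | 25.0 |
| 0 | 8 | 32 | 0 | 0.0 | 0.0 | 0.0 |

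Fourth row in full: A = 8/40 = 0.20 and P = 0.3, so the SAP gives 0.20 + 0.80 x 0.3 = 0.44. Hours lost are 8 + 0.3 x 8 = 10.4; 10.4/40 = 26% and 10.4/16 = 65%. The formulas agree with these differences: the excess over (i) is 24 x 0.3/40 = 18 points, and the shortfall from (ii) is 0.7 x (0.50 - 0.20) = 21 points.

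The first four rows share Q2, Q5 and T. On-the-job loss falls from 0.3 x 32 = 9.6 hours to 0.3 x 8 = 2.4 hours, yet the SAP score stays at 44.0.

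**The case against.** A reader might go further in three ways that the documents do not support.

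- That the score is wrong for anyone with unrelated time off. It is not. With Q2=0 and Q5=0 it is 0 on every reading. With Q2=0 it equals target (ii) whatever Q3 is, and with Q5=0 it equals target (i).
- That change from baseline moves with unrelated leave. At fixed Q2, Q5 and scheduled hours the SAP score does not move at all; both consistent alternatives do. The fault is insensitivity to how the remaining hours were spent. Movement would need a further assumption, for example that heart-related absence shrinks when other leave is taken.
- That Q3 is a transcription error and Q2/(Q2+Q4) is the correct absenteeism score. Settling that needs the instrument's scoring manual, which the SAP neither reproduces nor lists among its references. If a share of all scheduled hours was meant, the absenteeism score is coherent as it stands and only the combined score fails.

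The strongest defence is that the combined score is labelled as overall impairment and could be meant to apply the Q5 rate to all time not lost to the heart condition, worked or not. That can be interpreted, but the SAP does not say so, and the same label describes absenteeism plus presenteeism, with Q5 worded for time at work.

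The objection on importance largely stands. The larger discrepancies above assume that 50% to 60% of the week was unrelated leave, and nothing in the documents suggests that this is common. What also stands is that the direction of the error is undetermined until a denominator is chosen.

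**Conclusion.** The third WPAI formula is inconsistent with its own components whenever Q3>0 and, for a given subject, can give a wrong value. For Q2>0, Q3>0 and 0<Q5<10 it is wrong on either denominator: too high as a share of scheduled hours and too low as a share of Q2+Q4. With one unrelated day off in an illustrative 40-hour week (Q2=8, Q3=8, Q4=24, Q5=3) the discrepancy is 6.0 or 3.5 points. With three such days (Q3=24, Q4=8) it is 18 or 21 points.

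This rests on reading Absenteeism and Presenteeism as fractions and on taking Q5 at its wording, as impairment while at work. The size in the trial cannot be stated, because the documents give no distribution of Q3.

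The consequence is small. It touches employed subjects with unrelated leave in the seven-day recall, on a comparison made without multiplicity adjustment (SAP 9) for an endpoint that is secondary in Protocol 9.6.2 but absent from SAP 2.3.6. The primary endpoint, sample size and alpha are unaffected.

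**What to change.** State in SAP 9.4.3 which denominator is intended, define Absenteeism and Presenteeism as fractions inside the combined formula, and use one of two consistent versions:

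- Absenteeism = Q2/(Q2+Q4), with the combined score unchanged in form; or
- Absenteeism = Q2/(Q2+Q3+Q4) as now, with presenteeism weighted by Q4/(Q2+Q3+Q4) in place of (1 - Absenteeism).

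The choice should be deliberate, since the two move in opposite directions with unrelated leave: at fixed Q2, Q5 and scheduled hours, more leave raises the first and lowers the second. Make the edit together with the correction of the repeated factor of 100, which concerns the same line.

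The cost is one formula and its programming. All the items are already collected and listed, so scores can be recomputed without loss of data.

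### The WPAI work-productivity-loss formula in SAP 9.4.3 uses 0–100 scores as if they were proportions, so as written it returns values such as −93,000 where 60 is meant

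*SAP*

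**What the plan says.** SAP section 9.4.3 sets out four WPAI scores built from the questionnaire items. Written compactly:

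- Score 1, absenteeism: A = 100 × Q2 / (Q2 + Q3 + Q4).
- Score 2, presenteeism: P = 100 × Q5 / 10.
- Score 3, labelled "Work productivity loss (overall work impairment / absenteeism plus presenteeism"): 100 × (A + (1 − A) × P), with absenteeism and presenteeism referred to by the same names as scores 1 and 2.
- Score 4, activity impairment: 100 × Q6 / 10.

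The section fixes the scale and direction: "WPAI outcomes are expressed as impairment percentages, with higher numbers indicating greater impairment and less productivity". Scores 1 to 3 are restricted to subjects in employment. On use, it says that "only the 4 summary scores detailed above will be summarized", and the summaries are to carry p-values comparing change from baseline between treatment groups.

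Protocol section 9.6.2 lists change in the WPAI score among the secondary efficacy endpoints and refers to the SAP for detail. The lists in protocol section 2.4.1 and SAP section 2.3.6 do not include it.

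**The concern.** The term (1 − A) and the leading 100 in score 3 make sense only when A and P are proportions. As defined two lines earlier they are percentages, and no sentence converts them. A programmer who follows the text will produce values outside the 0–100 range for almost every employed subject with any absenteeism or presenteeism.

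The documents offer no second source to fall back on. For the SF-36 the SAP cites published scoring instructions; for the WPAI it cites none, so section 9.4.3 is the only scoring rule available. At stake is one planned efficacy comparison: its means, its changes from baseline and its p-value.

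**Working it through.** **Inputs.** The three formulas come from SAP 9.4.3 as set out above. The documents give no worked WPAI value, so there is no stated figure to reproduce. The responses below are assumed for illustration. For the main case: Q2 = 8 hours missed for the heart condition, Q3 = 0, Q4 = 32 hours worked, Q5 = 5.

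**Scores 1 and 2.**
- A = 100 × 8 / (8 + 0 + 32) = 20
- P = 100 × 5 / 10 = 50

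**Score 3 as written.**
100 × (20 + (1 − 20) × 50) = 100 × (20 − 950) = −93,000

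**Score 3 with A and P as proportions.**
100 × (0.20 + 0.80 × 0.50) = 60

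**Other cases.**

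| A | P | As written | Intended |
|---|---|---|---|
| 20 | 50 | −93,000 | 60 |
| 20 | 30 | −55,000 | 44 |
| 10 | 10 | −8,000 | 19 |
| 50 | 50 | −240,000 | 75 |
| 0 | 50 | 5,000 | 50 |
| 20 | 0 | 2,000 | 20 |

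**Full range.** Taking A from 0 to 100 in steps of 1 and P from 0 to 100 in steps of 10 gives 101 × 11 = 1,111 combinations. The written formula runs from −980,000 (A = 100, P = 100) to +10,000. Only 12 combinations fall within 0–100, and only 2 equal the intended score: A = 0, P = 0 and A = 1, P = 100.

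**Direction.** For fixed A, the written score changes by 100 × (1 − A) per point of P. This is negative whenever A exceeds 1; at A = 20 it is −1,900 per point. The intended score changes by (100 − A)/100 per point, which is +0.8 at A = 20. Take two subjects whose presenteeism improves from 50 to 30:

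- At A = 20 the intended change is 44 − 60 = −16. The written change is −55,000 − (−93,000) = +38,000, which reads as worsening.
- At A = 0 the intended change is 30 − 50 = −20. The written change is 3,000 − 5,000 = −2,000, which has the right sign but is 100 times too large.

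The same improvement therefore moves the written score in opposite directions, and the subject with absenteeism dominates any mean.

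**A partial repair does not work.** Dropping only the leading 100 still gives 20 + (1 − 20) × 50 = −930 at A = 20, P = 50.

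**The case against.** The best counter-argument is that the intended meaning can be recovered from the section itself. The form of score 3 is right if A and P are proportions, and a result of −93,000 so plainly contradicts the statement that outcomes are impairment percentages that nobody would report it. On this view it is a slip of notation, one name serving for both the percentage and the proportion, and the quality-control checks required by SAP section 13.3 before the final analysis would catch it.

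Much of that is fair. A competent programmer would probably notice, and the intended score is not in doubt. But the written rule remains wrong. Correcting it silently means departing from the SAP without a record, and independent programming checked against the text would not agree with the corrected output. Section 13.3 does not mention checks of derived scores.

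Two limits on scope also stand. Score 3 exists only for employed subjects. The written and intended values can also coincide by accident when absenteeism is about 1%, as at A = 1, P = 100, though this has no practical weight.

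A misread PDF is an unlikely explanation. The factor of 100 appears in scores 1, 2 and 4 alike and agrees with the sentence on percentages.

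**Conclusion.** The concern holds. As written, score 3 is wrong for essentially every employed subject with non-zero absenteeism or presenteeism. The size depends on the responses: 100 times too large when either score is zero, and negative by tens or hundreds of thousands in ordinary mixed cases. With absenteeism above 1% it also moves the wrong way with presenteeism.

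This rests on reading the formula literally, with score names meaning the scores just defined. The numerical examples use assumed responses.

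The importance is low. One of four WPAI scores is affected; the other three are correctly written. WPAI appears as a secondary endpoint only in protocol section 9.6.2, non-primary efficacy tests carry no multiplicity adjustment, and trial success depends on infarct size alone. Neither the primary result nor the safety conclusions change.

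**What to change.** In SAP section 9.4.3, replace the third formula with

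100 × [A/100 + (1 − A/100) × P/100],

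where A and P are the percentage scores from formulas 1 and 2. The equivalent form A + (100 − A) × P/100 would do as well. For A = 20, P = 50 it gives 20 + 80 × 0.50 = 60; for A = 20, P = 30 it gives 20 + 80 × 0.30 = 44; for A = 0, P = 50 it gives 0 + 100 × 0.50 = 50. The score stays within 0–100 and rises with impairment, as the section requires.

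The change is to a single line. It needs no new data, alters no other analysis and has no downside.
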